1.0 Study Summary

Study Title	Objective Assessment of Pain Thresholds in Women with Vulvodynia
Study Design	Clinical Trial
Primary Objective	Develop annotated pain maps showing region and size of area sensitive to mechanical stimulus. The pain maps will be created by combining IR images, photographs, and clinical input, and will be correlated with patient co-morbidities.
Secondary Objective(s)	a-Determine changes in the location and size of sensitive regions following various conventional clinical interventions for vulvodynia. b-Develop a large, information-rich database of annotated pain maps from patients, and use Artificial Intelligence to identify patterns and trends.
Research Intervention(s)/ Investigational Agent(s)	Infrared imaging of the vulva and assessment of pain intensity using cotton-tipped swab.
IND/IDE #	N/A
Study Population	Women with vulvodynia and healthy controls
Sample Size	60 women (30 in each group)
Study Duration for individual participants	One day 1 hour

Study Specific Abbreviations/ Definitions	
--	--

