12.0 Procedures Involved*

12.1 Provide a description of **all research procedures or activities** being performed and when they are performed once a subject is screened and determined to be eligible. Provide as much detail as possible.

NOTE: This should serve as a blueprint for your study and include enough detail so that another investigator could pick up your protocol and replicate the research. For studies that have multiple or complex visits or procedures, consider the addition of a schedule of events table in in your response.

Response:

All procedures will be performed on the same day as screening and consent and are expected to take 30-60 minutes. An annotated pain map of the vulva will be created based on subjective assessment of pain, and thermographic imaging.

- A. Images and Thermographic readings will be taken with an infrared camera prior to any physical contact with the vulva of the patient other than by placing a calibrated paper drape circumferentially on the vulva outside of the area of interest. The drape will be calibrated to maintain pain map/image size comparison between patients.
- B. Subjective pain at several predetermined loci will be assessed with a cotton swab (standard of care) and rated on a Likert scale of 0-10. This data will be added to the thermographic map.
- C. Comparative analysis of the two measures will be performed (separate from visit). Patient demographic and health data (see table below) will be collected by direct participant interview and review of the patient's chart in Allscripts.

12.2 Describe what data will be collected.

NOTE: For studies with multiple data collection points or long-term follow up, consider the addition of a schedule or table in your response.

Response:

Patient Name

DOB

MR#

Date of Visit

Vulvar images, both plain and infrared.

Pain sensitivity data on a Likert scale of 0-10 using cotton-tipped swabs.

Status (PWD or Control)

Race

Gravida

Para

Vaginal Births

Cesarean Births

Sexually Active

Dyspareunia

Smoking

Marital Status

Education Level

Medical History

Depression

Anxiety

Fibromyalgia

Chronic Pelvic Pain

Interstitial Cystitis

Endometriosis

Irritable Bowel Syndrome

TMJ

Other

h/o yeast infections

h/o BV

h/o abuse

PWD Patients Only

Symptom Duration

Pain Map Score

Pain Diary Score

FSDS

Previous Rx (Y/N)

Previous Rx (type)

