19.0 Data Management and Analysis*

19.1 *Describe the data analysis plan, including any statistical procedures. This section applies to both quantitative and qualitative analysis.*

Response: Both visible and infrared images will be acquired using our state-of-the-art FLIR E-95 camera. The E-95 is one of the best IR cameras available. It has very high spatial resolution and temperature sensitivity. In summation: if there is any correlation between temperature and vulvodynia, this camera will be able to see it. The camera's software stores both of these images along with metadata in a single jpeg. We have already designed our own custom software to extract the raw temperature data from these files. Our software will control the camera remotely through a USB link. This, along with mounting the camera on a tripod, will ensure that there is minimal "smearing" of the image due to small uncontrollable movements of the person operating the camera. This will give us the highest accuracy possible. In addition, our graphical software interface will allow the user to mark the image to indicate where sensitivity to pressure or an increase in thermal activity was observed. As we expect spatial variation in temperature from the affected area to the unaffected, we will provide the user with a variety of options for subtracting the average body temperature to make the difference more visible. All data will be stored securely to maintain patient confidentiality. Once we have collected enough data, we can begin the process of establishing the metrics by which we can diagnose the patients. Considering all of our data (pressure, temperature, color (from visible light image)) we can determine the connection of each to a positive diagnosis and assign a finally probability to our result.

19.2 *If applicable, provide a power analysis.*

NOTE: This may not apply to certain types of studies, including chart/records reviews, survey studies, or observational studies. This question is asked to elicit whether the investigator has an adequate sample size to achieve the study objectives and justify a conclusion.

Response: This is a pilot study. No power analysis will be performed.

19.3 *Describe any procedures that will be used for quality control of collected data.*

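### Section 19.1 develops diagnostic metrics and a probability of diagnosis from the study's only 60 women and describes no validation, so any accuracy taken from that fit would be optimistic by an unknown amount

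*Combined protocol and SAP*

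**What the plan says.** Section 19.1 is the whole analysis plan. On diagnosis it says: "Once we have collected enough data, we can begin the process of establishing the metrics by which we can diagnose the patients". The inputs and output follow: "Considering all of our data (pressure, temperature, color (from visible light image)) we can determine the connection of each to a positive diagnosis", ending with a probability attached to the result.

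Three other statements bear on how much freedom the fitting has:

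- Background correction of the images is left to the user (Section 19.1): "we will provide the user with a variety of options for subtracting the average body temperature to make the difference more visible". The same user marks regions on the image by hand.
- Section 1.0, secondary objective b, plans a large database of pain maps and will "use Artificial Intelligence to identify patterns and trends".
- Section 12.1 says "Subjective pain at several predetermined loci will be assessed with a cotton swab". The number of loci is not given.

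The sample is 60 women, 30 with vulvodynia and 30 controls (Sections 1.0 and 7.1), with one visit each (Section 13.2). Section 19.2 says: "This is a pilot study. No power analysis will be performed". The protocol does not mention a hold-out set, cross-validation, bootstrap correction, an external sample, a pre-specified model or a pre-specified cut-off.

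**The concern.** Turning several measurements into a probability of diagnosis is the development of a prediction model. A model fitted to a small sample adapts to chance differences between the two groups. If its accuracy is then computed in the women used to fit it, the figure is too high on average, even when the inputs carry no information. The excess grows with the number of inputs, regions, background subtractions and cut-offs tried. The plan limits none of these, and it does not say how much data is enough to start.

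A pilot's main product is a judgement on whether the technique merits further work. An uncorrected AUC or accuracy could make uninformative temperature and colour data look useful, and the reader would have no means of separating signal from overfitting in that figure.

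**Working it through.** **The plan's own figures.** There is no accuracy target, AUC, alpha, power or effect size to reproduce. The only number is the sample size, and 2 x 30 = 60 is consistent.

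**Inputs.** From the documents: 30 v 30, one visit, three data types (pressure, temperature, colour). Assumed, because the documents do not give them: the number of inputs p (shown as a range), a linear discriminant as the model, and independent normal inputs with no difference between groups. The true AUC and accuracy are then both 0.50.

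**Step 1: one input, by formula.** The null variance of the AUC is (n1 + n0 + 1)/(12 x n1 x n0) = 61/10800 = 0.00565, so the SD is 0.075. If the direction of the marker is chosen from the data, the mean apparent AUC is 0.5 + 0.075 x sqrt(2/pi) = 0.5 + 0.075 x 0.798 = 0.56.

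**Step 2: more inputs, by simulation.** Fit the discriminant to 60 women and score the same 60 (apparent performance). Then apply 10-fold cross-validation by woman, refitting in each fold.

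| Inputs p | Mean apparent AUC | Mean apparent accuracy | Cross-validated accuracy |
|---|---|---|---|
| 3 | 0.62 | 58% | about 50% |
| 10 | 0.73 | 67% | about 50% |
| 20 | 0.84 | 76% | about 50% |
| 32 | 0.94 | 86% | about 50% |

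In new women the mean AUC of the same fitted rules is about 0.50. The 5th to 95th percentile of apparent AUC is 0.54 to 0.71 with 3 inputs and 0.65 to 0.82 with 10. The 3-input row stands for one score per listed data type. The 32-input row stands for 8 sites with temperature and three colour channels each (8 x 4 = 32), a layout the documents do not state.

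**Step 3: choosing a cut-off alone.** With equal groups, accuracy at the best cut-off is 0.5 + J/2, where J is the largest gap between the two groups' cumulative distributions. For one null marker, mean J = 0.21, so accuracy is 0.5 + 0.105 = 0.61. For the best of 10 null markers, mean J = 0.326, so accuracy is 0.5 + 0.163 = 0.66.

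**Step 4: adding null image features to an informative pressure score.** Assume pressure differs by 1 to 2 SD between groups (AUC 0.76 to 0.92 alone). Ten null temperature and colour features then appear to add 0.083 to 0.032 to the AUC. In new women they lower it by 0.068 to 0.040.

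**Step 5: precision after correction.** The Hanley-McNeil standard error is sqrt{[A(1-A) + 29(Q1-A²) + 29(Q2-A²)]/900}, with Q1 = A/(2-A) and Q2 = 2A²/(1+A). At A = 0.5, 0.7 and 0.8 it is 0.075, 0.068 and 0.058. Multiplied by 1.96, the 95% half-widths are about 0.15, 0.13 and 0.11. These treat the score as fixed, so they are a guide only.

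**The case against.** Several stronger readings are tempting, and the documents do not support them.

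- **That the plan judges its metrics in the same 60 women.** No accuracy measure and no evaluation step is written. Silence on validation is a gap, not a stated choice of re-substitution. What stands is that these women are the only data the protocol provides for fitting or checking a rule.
- **That the result will look good even if temperature and colour are uninformative.** This depends on the number of inputs. At the one count the text suggests, three data types, the null AUC is about 0.62: inflated, but not impressive. Section 19.1 could also mean one-at-a-time associations.
- **That each woman supplies temperature and colour at several loci.** Section 12.1 uses the loci for swab pain only. Temperature and colour come from images, and no extraction per locus is described, so the 24-to-32-input range is hypothetical.
- **That artificial intelligence will be run on the same data.** Section 1.0 refers to a large database. The concern applies only if these women are used for training.
- **That the study's main result is at risk.** The primary objective is annotated pain maps (Section 1.0), and the endpoint compares thermographic evidence between groups (Section 3.1). Neither is diagnostic accuracy.

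The pilot label explains the missing power analysis. It does not remove bias from a performance figure. Correlation between inputs does not help either: with pairwise correlation 0.5, the null apparent AUCs were 0.62, 0.74, 0.88 and 0.94 for 3, 10, 24 and 32 inputs.

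Pressure raises a separate matter. Section 4.1 describes the swab test as part of the clinical diagnosis, so a combined probability could look good through pressure alone. Cross-validation would not remove that.

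**Conclusion.** The point holds in a limited form. The plan commits to diagnostic metrics and a probability from 60 women and describes no internal or external validation. Any accuracy taken directly from that fit would be optimistic on average. With no true signal, the mean apparent AUC is 0.06 too high with 1 input, 0.12 with 3, 0.23 with 10 and 0.44 with 32. These sizes rest on a linear discriminant, independent null inputs and assumed input counts. Because the plan fixes no feature set, it puts no ceiling on the bias.

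This should be fixed before analysis. It is not critical, because the primary objective and the stated endpoint do not depend on it.

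**What to change.** Keep the two sentences in Section 19.1, since they are the only statement of the inputs and of the probability output, and add:

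> Metrics will be derived once, after enrolment and data collection have closed. AUC, accuracy and calibration will be reported as bootstrap optimism-corrected or repeated 10-fold cross-validated values with 95% confidence intervals. Resampling is by woman, never by image or locus, and every data-driven step (region, subtraction option, feature choice, cut-off) is repeated inside each resample. Results will be shown for temperature and colour without pressure as well as for all inputs. Apparent values will not be reported as performance, and the results are exploratory until tested in new patients.

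The same rule should cover any AI classifier trained on these women. The trigger is the close of data collection, not completion of all 60, because Section 22.3 provides for destroying the data of a control who cannot complete the procedures. A small feature set and a single background subtraction, both fixed in advance, would reduce the optimism at source.

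The cost is protocol wording and some analyst time, with no extra patients, visits or procedures. The reported accuracy will be lower than the naive figure, and its interval will be wide: an AUC half-width of about 0.11 to 0.15 at 30 v 30.

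### Colour from the photograph is a planned diagnostic input, but it is not standardised within or between images, and skin tone could confound it

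*Combined protocol and SAP*

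**What the plan says.** **Use of colour.** Section 19.1 lists the inputs as "Considering all of our data (pressure, temperature, color (from visible light image" and continues that "we can determine the connection of each to a positive diagnosis and assign a finally probability to our result". No model, covariate or adjustment is named.

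**How the image is taken.** Section 19.1 states that "Both visible and infrared images will be acquired using our state-of-the-art FLIR E-95 camera" and that "The camera's software stores both of these images along with metadata in a single jpeg". Mounting the camera on a tripod and controlling it by USB "will ensure that there is minimal 'smearing' of the image due to small uncontrollable movements of the person operating the camera". Section 12.1 A places the images "prior to any physical contact with the vulva of the patient other than by placing a calibrated paper drape". Of the drape it says: "The drape will be calibrated to maintain pain map/image size comparison between patients".

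**Normalisation.** For temperature, section 19.1 says "we will provide the user with a variety of options for subtracting the average body temperature to make the difference more visible". Nothing similar is offered for colour.

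**Groups.** Section 1.0 gives 30 women per group. Under section 11.1 the principal investigator approaches affected women who attend for vulvar pain, while controls are approached through their own provider before a routine annual exam. No matching is described. Race is on the data list in section 12.2, but no use of it is stated and skin tone is not recorded. The answer on data quality control (section 19.3) concerns the selection of patients, not images.

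**The concern.** The colour recorded in a photograph depends on the light, the exposure, the white balance and the pigmentation of the skin, as well as on any inflammation. Without a reference in the frame, these contributions cannot be told apart afterwards. Each woman has one study visit (section 13.2), so an image taken without a reference cannot be reliably corrected later.

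Two consequences follow, and they differ in kind. Lighting that varies from visit to visit without regard to group makes colour noisier and weakens whatever signal it carries. A difference in skin-tone mix between the groups could instead produce a colour difference that has nothing to do with vulvodynia. The diagnostic probability in section 19.1, and any pattern-finding in the planned database that draws on colour, could then absorb it as a sign of disease. More participants would reduce the noise but not that bias.

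**Working it through.** The plan gives no alpha, effect size, SD or power for colour, and section 19.2 states that no power analysis will be done. There is therefore no figure of the plan's own to reproduce. The check has two parts.

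**1. What each stated control covers**

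| Control | Where | Acts on colour? |
|---|---|---|
| Calibrated drape | 12.1 A | No, size only |
| Tripod and USB control | 19.1 | No, motion blur |
| Subtraction of average body temperature | 19.1 | No, thermal data only |
| Imaging before contact | 12.1 A | Partly: rules out redness from the swab |
| One suite, one named camera | 14.1, 19.1 | Partly: limits variation, but no room, light or setting is fixed |
| Race recorded | 12.2 | Only if used, and no use is stated |

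No section sets lighting, exposure, white balance or a colour reference.

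**2. How much a shift unrelated to disease could matter (illustration)**

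Inputs: n = 30 per group (section 1.0). Assumed: a two-sided 5% two-sample t-test, no disease effect on colour, and a between-group shift of d SD from other causes.

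- Noncentrality = d × √(n/2) = d × √15; degrees of freedom 58; critical value 2.002.
- Apparent discrimination: AUC = Φ(d/√2).

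| Assumed d | Noncentrality | P(test positive) | Apparent AUC |
|---|---|---|---|
| 0 | 0 | 0.05 | 0.50 |
| 0.25 | 0.968 | 0.159 | 0.57 |
| 0.5 | 1.936 | 0.478 | 0.64 |

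(The normal approximation gives 0.162 and 0.491 for the last two rows.)

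For skin tone specifically, let darker skin make up shares p₁ and p₂ of the two groups, and let the tones differ by D within-tone SD in recorded colour. The mean shift is D × |p₁ − p₂|. The variance in group i is 1 + D²pᵢ(1 − pᵢ), and SE = √[(v₁ + v₂)/30]. The probabilities use the normal approximation.

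- 10% v 30%, D = 2: shift 2 × 0.2 = 0.4; v₁ = 1.36, v₂ = 1.84; SE = √(3.20/30) = 0.327; ratio 1.22; P = 0.23. For D = 1 and 3, P = 0.11 and 0.33.
- 20% v 30%, D = 1, 2, 3: P = 0.06, 0.09, 0.11.

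The shares and D are assumptions, because the documents give none. The effect runs from negligible to substantial according to how far the groups differ in skin tone.

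**The case against.** **Colour is peripheral.** The endpoint in section 3.1 is thermographic, the hypothesis in section 2.2 concerns pain sensitivity and thermography, and colour appears as a diagnostic variable in one sentence of section 19.1, about metrics still to be established in a pilot. This stands, and it limits the point to the diagnostic probability and to database work that uses colour.

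**Lighting that differs by group is not shown.** A reader might infer from the separate recruitment routes that cases and controls are photographed under different light. The documents do not support that. Section 11.1 describes who approaches the women, not where they are imaged. Section 14.1 names one suite for data acquisition and section 19.1 one camera model, on a tripod. This stands; lighting counts here mainly as a source of noise.

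**The figures are not specific to colour.** Any confounder shifting any variable by the same SD would give them, and section 19.1 contains no colour t-test. This also stands: they illustrate sensitivity at 30 v 30 and do not estimate a bias.

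**The unused race data and unmatched controls are general gaps.** Section 19.1 specifies no adjustment for anything. That is true, but the missing colour standard is a separate gap, and it cannot be repaired once imaging is done.

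A reader might also infer that images without a colour standard cannot be pooled at all. That goes too far. Colour becomes less comparable between images, but the photographs still serve for location, size and overlay on the pain map.

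**Conclusion.** The point holds in a limited form. Colour is a named input to the diagnostic probability, and nothing in the plan standardises it between images or refers it to the woman's own skin, although the plan does the latter for temperature. Lighting would mainly add noise. Skin tone could confound the case-control comparison, but the documents do not show that it differs between the groups, so the bias is possible rather than demonstrated and its size is unknown. The range of about 16% to 48% rests entirely on an assumed shift of 0.25 to 0.5 SD and on a nominal test that the plan does not contain; with a small skin-tone imbalance the inflation is slight. The thermographic endpoint and the use of photographs for location and size are untouched. The change is worth making before imaging starts, because each woman is imaged at a single visit.

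**What to change.** **Section 12.1 A.** Add neutral-grey and colour patches to the drape, and state a fixed light source, exposure and white balance.

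**Section 19.1.** Correct each image to the patches. Analyse colour as the difference between each locus and unaffected skin in the same woman. Check the result with adjustment for the race data already collected, reported as a coarse proxy for skin tone.

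**Alternative.** If this is not done, label colour exploratory and leave it out of the diagnostic probability.

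**Cost and limits.** The cost is a small change to the drape, a colour-correction step in the software (section 19.1 describes no colour processing at present), protocol wording and a little more analysis. The patches correct for illumination, not pigmentation. The within-woman contrast removes a constant offset in skin tone but may leave differences in how visible redness is on darker or lighter skin, which is why the adjusted check is needed. Sample size and visit schedule do not change.

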Vulvodynia is a heterogeneous group of clinical conditions defined by the [International Society for the Study of Vulvovaginal Disease](#) as chronic vulvar discomfort or pain, characterized by burning, stinging, irritation or rawness of the female genitalia [1]. The true prevalence is unknown but is estimated at 9-12% of the adult female population, with up to 2 million women affected. These chronic conditions cause significant burden in terms of quality of life and relationship dysfunction, especially for women with provoked vestibulodynia (pain at the opening of the vagina (“vestibule”) with vaginal penetration or attempted vaginal penetration) which interferes with normal sexual function [2]. This is a “hidden” women’s issue that is under-reported and under-treated because it causes embarrassment and feelings of inadequacy. The clinical management of localized, provoked vulvodynia has been disorganized and somewhat arbitrary [3]. Studies suggest that most women see a variety of providers over the course of months to years before the condition is diagnosed correctly. Diagnosis of these conditions is based on clinical picture, absence of other causes, and physical exam. During the exam, a cotton-tipped swab is used to assess for areas of tenderness and the patient is asked to rate her level of pain on a Likert scale. This has been the standard of care for many years, but reproducibility has not been assessed. In addition, monitoring response to therapy is also very subjective. Even return to sexual activity is not a reliable indicator of patient’s pain, since many women will continue to engage in sexual activity to avoid relationship discord. We have been developing a novel medical technique for the diagnosis and classification of vulvodynia. The technique will quantitatively measure mechanical sensitivity to touch/pressure simultaneously with thermal indicators of inflammation. The technique builds on current methodology used in assessment and knowledge about the known pathophysiology of the disorder. Through this combination of measurements, we plan to expand the diagnostic tools used in patient care as well as on the classification of this heterogeneous disorder.

4.2 *Include complete citations or references.*

Response:

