5.0 Study Design*

5.1 *Describe and explain the study design (e.g. case-control, cross-sectional, ethnographic, experimental, interventional, longitudinal, observational).*

Response:

Prospective study of women with vulvodynia and normal controls. We plan to evaluate a novel technique that quantifies both pain intensity and records thermographic changes of the vulva in women with a clinical diagnosis of provoked vulvodynia and normal controls. The study subjects will have a new or prior diagnosis of provoked vulvodynia and will be invited to participate in this evaluation. Women with prior diagnosis of vulvodynia will be symptomatic and untreated at the time of assessment. Control subjects will be unaffected women presenting for routine care who do not have vulvar pain or other active vulvar or vaginal disorder as these may interfere with thermographic mapping.

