8.0 Inclusion and Exclusion Criteria*

8.1 *Describe the criteria that define who will be **included** in your final study sample.*

NOTE: This may be done in bullet point fashion.

Response:

Women > 18 years of age

Women seeking care for vulvar pain

Controls: Women seeking routine gynecologic care

8.2 *Describe the criteria that define who will be **excluded** from your final study sample.*

NOTE: This may be done in bullet point fashion.

Response:

Women < 18 years of age

Pregnancy

Women with vulvar or vaginal disorder other than pain

8.3 *Indicate specifically whether you will include any of the following special populations in your study using the checkboxes below.*

NOTE: Members of special populations may not be targeted for enrollment in your study unless you indicate this in your inclusion criteria.

Response:

- Adults unable to consent
- Individuals who are not yet adults (infants, children, teenagers)
- Pregnant women
- Prisoners

8.4 *Indicate whether you will include non-English speaking individuals in your study. Provide justification if you will exclude non-English speaking individuals.*

*In order to meet one of the primary ethical principles of equitable selection of subjects, non-English speaking individuals may **not** be routinely excluded from research as a matter of convenience.*

In cases where the research is of therapeutic intent or is designed to investigate areas that would necessarily require certain populations who may not speak English, the researcher is required to make efforts to recruit and include non-English speaking individuals. However, there are studies in which it would be reasonable to limit subjects to those who speak English. Some examples include pilot studies, small unfunded studies with validated instruments not available in other languages, studies with numerous questionnaires, and some non-therapeutic studies which offer no direct benefit.

Response:

Non-English speakers are not eligible for inclusion in the study. This is a non-therapeutic study which will offer no direct benefit.

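### A probability taken from 30 diagnosed cases and 30 pain-free controls is not a diagnostic probability for women with vulvar pain; section 19.1 should report discrimination instead

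*Combined protocol and SAP*

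**What the plan says.** Section 19.1 describes the camera and software, then says that once enough data are in hand the team can start to set the metrics for diagnosing patients. Of the pressure, temperature and colour data it says that "we can determine the connection of each to a positive diagnosis and assign a finally probability to our result". It names no model, threshold, prior, calibration or validation step.

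The sample is fixed in the Study Summary (section 1.0) at "60 women (30 in each group"). Section 5.1 defines the two groups. For cases: "The study subjects will have a new or prior diagnosis of provoked vulvodynia". For controls: "Control subjects will be unaffected women presenting for routine care who do not have vulvar pain or other active vulvar or vaginal disorder". Section 8.2 also excludes "Women with vulvar or vaginal disorder other than pain", with no restriction to one group.

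The only prevalence in the protocol is in section 4.1: "The true prevalence is unknown but is estimated at 9-12% of the adult female population".

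**The concern.** A probability of disease depends on how common the disease is among those tested, and on how the test behaves in those who do not have it. In this study the first is a recruitment quota. The second is observed only in women for whom the diagnosis would not be in question, because they have no vulvar pain.

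Section 2.1 says the technique is meant to add to the diagnostic means available in patient care. There the question is whether a woman with vulvar pain has vulvodynia or something else, and section 4.1 says that the diagnosis rests partly on ruling out other explanations. The study has no women whose vulvar pain has another explanation. A reader given a final probability from these data could take it as the chance of vulvodynia in such a patient, which the data cannot supply.

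**Working it through.** **The plan's own figures.** 30 + 30 = 60, which agrees with section 7.1. The case share is 30/60 = 50%, by design. The protocol gives no sensitivity, specificity or probability, and section 19.2 states that no power analysis is done, so there is no further figure to reproduce.

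**Step 1: the case share.** The probability of disease after a positive result is

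PPV = Se × p / [Se × p + (1 − Sp) × (1 − p)],

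where p is the share with disease among those tested. In the study p = 0.50. Moving to another p multiplies the study odds by p/(1 − p). At the section 4.1 figures this divides the odds by 0.91/0.09 = 10.1 or by 0.88/0.12 = 7.3.

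Se and Sp are assumptions, shown as a range. The 30% and 70% columns are also assumptions, because the protocol gives no prevalence among women seeking care for vulvar pain.

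| Assumed Se = Sp | p = 50% (this sample) | 9% | 12% | 30% (assumed) | 70% (assumed) |
|---|---|---|---|---|---|
| 0.70 | 0.700 | 0.187 | 0.241 | 0.500 | 0.845 |
| 0.80 | 0.800 | 0.283 | 0.353 | 0.632 | 0.903 |
| 0.90 | 0.900 | 0.471 | 0.551 | 0.794 | 0.955 |

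Worked case at 0.80:
- p = 0.09: 0.072/(0.072 + 0.182) = 0.283
- p = 0.12: 0.096/(0.096 + 0.176) = 0.353
- p = 0.30: 0.24/(0.24 + 0.14) = 0.632
- p = 0.70: 0.56/(0.56 + 0.06) = 0.903

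The study figure is too high if the target prevalence is below 50% and too low if it is above.

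**Step 2: who the controls are.** Specificity is the share of women without vulvodynia who test negative. Here all of them are pain-free and have no other active vulvar or vaginal disorder. Section 5.1 gives the reason: such conditions could disturb the thermographic map. That is also a reason to expect that specificity may differ in women who have them. Section 8.1 lists women seeking care for vulvar pain without naming a diagnosis, but section 5.1 requires the diagnosis and the status field in section 12.2 has only two values, so no third group exists. The columns above change p but keep the same Sp, so re-weighting does not repair this.

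**Step 3: an input that is part of the diagnosis.** Section 4.1 describes the swab examination for tenderness as part of how the diagnosis is reached. Section 19.1 lists pressure among the inputs. A measure that helped to define the cases will separate them from pain-free women partly by construction, so accuracy that includes the swab score is likely to be inflated.

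**Step 4: precision.** With 30 controls, 24 negative (0.80) gives an exact 95% interval for specificity of 0.61 to 0.92. Even 30 of 30 negative gives a lower limit of 0.025^(1/30) = 0.88. Any accuracy figure needs its interval.

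**The case against.** A reader might infer that the promised probability is bound to be far too high, by setting 80% against 28-35%. The documents do not support that. The 9-12% refers to adult women in general, and the same sentence calls the true prevalence unknown. Nothing in the protocol proposes screening that population. Affected women are recruited when they attend for vulvar pain (section 11.1), and prevalence among them is not given. If it exceeds 50%, the error changes sign. The 9-12% figures also apply a specificity from women selected to have no vulvar disorder to a population that includes such disorders, so they are illustrations and not corrected values.

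A reader might also infer that the plan commits to an uncorrected 50:50 estimate. It does not say so. No estimator is named, and an external prior could still be used. The word probability could even mean statistical confidence, though beside talk of diagnosing patients that is the less natural reading.

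Other points in the plan's favour are fair. The stated primary objective is pain maps, the endpoint in section 3.1 and the hypothesis in section 2.2 are openly comparisons with unaffected women, and pain-free controls are a reasonable first step for a pilot. Section 2.1 makes no probability claim. Section 12.5 says individual results are not shared, so the figure has no stated route into a participant's care.

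These points limit the tone and the size of the claim. They do not supply a target population, a pre-test probability or a suitable comparison group for the probability in section 19.1.

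**Conclusion.** The concern holds in a limited form. A probability drawn from this sample is not a diagnostic probability for any population the protocol describes. Unless corrected, it carries a 50% case share that comes from the quota, and at any prevalence it rests on specificity seen only in pain-free women.

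The size of the prevalence part cannot be fixed from the documents. At an assumed 0.80 for sensitivity and specificity, the in-sample 80% corresponds to anything from 28% (at 9%) to 90% (at an assumed 70%). The claim that the figure is certainly too high, or too high by a known amount, is not established. The conclusion assumes that section 19.1 means a probability of diagnosis. If it means something else, the sentence needs clarifying anyway. The study design can stand and the data remain usable. What needs to change is the reported quantity and the conclusion drawn from it.

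**What to change.** In section 19.1:

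1. Replace the final probability with sensitivity, specificity and likelihood ratios, or AUC, with confidence intervals, for women with provoked vulvodynia against pain-free controls.
2. Report the image measures (temperature, colour) separately from the swab pain score.
3. If a probability is shown at all, give it over a stated and labelled range of pre-test prevalences, not from the 30:30 mix, and note that specificity comes only from pain-free women.
4. Limit the conclusion to distinguishing women with provoked vulvodynia from pain-free women.

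Section 2.1 needs no edit. The cost is a few sentences and one short calculation, with no new participants, procedures or data. The downside is a narrower and less favourable headline claim.
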